### Post-treatment Emergent Adverse Events

A post-treatment emergent adverse event is any AE occurring after the time of residual drug effect of the IMP, i.e. after the last assessment on Day 4 in Part1, and after Day 2 in Part 2.

## **8.2 Collection and Recording of Adverse Events**

### **8.2.1 Collection of Adverse Events**

The Investigator must monitor the condition of the subject throughout the trial from the time of obtaining informed consent until the last visit.

The sources of AEs cover:

- The subject's response to questions about his/her health (a standard non-leading question such as "How have you been feeling since your last visit?" is asked at each visit).
- Symptoms spontaneously reported by the subject.
- Investigations and examinations where the findings are assessed by the Investigator to be clinically significant changes or abnormalities.
- Other information relating to the subject's health becoming known to the Investigator (e.g. hospitalisation).

### **8.2.2 Recording of Adverse Events**

The Investigator must record all AEs in the Adverse Event Log provided in each subject's eCRF with information about:

- AE
- Date and time of onset (time can be omitted, if applicable)
- Intensity
- Causal relationship to IMP
- Action taken to IMP
- Other action taken
- Date and time of outcome (time can be omitted, if applicable)
- Outcome
- Seriousness.

Each of the items in the Adverse Event Log is described in detail in the following sections.

### **Adverse Event**

Adverse events should be recorded as diagnoses, if available. If not, separate signs and symptoms should be recorded. One diagnosis/symptom should be entered per record.

If a subject suffers from the same AE more than once and the subject recovers in between the events, the AEs should be recorded separately. If an AE changes in intensity, a worst-case approach should be used when recording the event, i.e. the highest intensity and the longest duration of the event. However, if an AE with onset before the first IMP administration (i.e. a pre-treatment adverse event) changes in intensity, this must be recorded as two separate events. The initial AE should be recorded with outcome “not yet recovered” and the date and time of outcome is when the intensity changed. The second AE should be recorded with date and time of onset when the intensity changed.

Note the following: A procedure is not an AE; the reason for conducting the procedure is. Hospitalisation is not an adverse event; the reason for hospitalisation is. Death is not an adverse event, but the cause of death is (an exception is sudden death of unknown cause, which is an adverse event).

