HVPG will be the primary pharmacodynamic parameter and assessments will be performed before, during, and immediately after the intravenous administration on Day 3. Patients will be confined to the clinic during the treatment period and will be carefully monitored for adverse events and effects on systemic haemodynamics.

A Safety Review Committee (SRC) will evaluate the safety, tolerability, and pharmacodynamics of the compound after the completion of Part 1 to recommend what dose of FE 204205 to evaluate in Part 2.

Part 2 is a placebo controlled, double-blind, randomised investigation evaluating the effects of a single dose of FE 204205 on portal haemodynamics and will include 16 patients receiving FE 204205 and 4 patients receiving placebo. Each patient will receive a 2-hour intravenous infusion of the maximum tolerated dose of FE 204205 as defined in Part 1, or placebo, on Day 1. Systemic and portal haemodynamics will be assessed by pulmonary artery and hepatic vein catheterization. HVPG will be the primary pharmacodynamic parameter and assessments will be performed before,

during, and immediately after the intravenous administration. Patients will be confined to the clinic during the treatment period and will be carefully monitored for adverse events and effects on systemic haemodynamics.

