#### Treatment Emergent Adverse Event

A treatment emergent adverse event is any AE occurring after the administration of the IMP and within the time of residual drug effect, or a pre-treatment adverse event or pre-existing medical condition that worsens in intensity after administration of the IMP and within the time of residual drug effect.

The time of residual drug effect is the estimated period of time after the administration of the IMP, where the effect of the product is still considered to be present based on pharmacokinetic (PK), pharmacodynamic (PD) or other substance characteristics. The residual drug effect is generally accepted to be 5 times the terminal half-life. The terminal half-life of FE 204205 is anticipated to be within the range of 3 hours, i.e. in this study the residual drug effect is likely to be well within the time to the last assessment in both Part 1 and Part 2. Since this is the first time FE 204205 is administered to patients with cirrhotic portal hypertension, all AEs occurring from start of infusion on Day 1 up to the last assessment on Day 4 in Part 1 and Day 2 in Part 2 are regarded as treatment emergent.

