#### **9.6.2.4      Adverse events**

Adverse events (AE) will be coded according to the latest version of MedDRA. All data will be listed by subject. Only treatment emergent AEs will be presented in summary tables. Separate data listing will be provided for AEs that are defined as pre-treatment or post-treatment emergent.

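### The two-record rule for pre-treatment AEs has no direction, so an AE that eases after the infusion starts can be tabulated as treatment emergent

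*Combined protocol and SAP*

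**What the plan says.** **Recording (section 8.2.2, Adverse Event).** In general, an AE that changes in intensity stays as one record at its worst grade. An AE that began before the first IMP administration is the exception: "i.e. a pre-treatment adverse event) changes in intensity, this must be recorded as two separate events". The first record is closed as not yet recovered at the time of the change. For the other, "The second AE should be recorded with date and time of onset when the intensity changed".

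**Classification (section 8.1, Treatment Emergent Adverse Event).** The definition has two limbs. The general one reads "A treatment emergent adverse event is any AE occurring after the administration of the IMP and within the time of residual drug effect". The one for events already present reads "or a pre-treatment adverse event or pre-existing medical condition that worsens in intensity after administration of the IMP". A trial-specific rule then makes treatment emergent "all AEs occurring from start of infusion on Day 1 up to the last assessment on Day 4 in Part 1 and Day 2"; the Day 2 limit is the one for Part 2. Later events are post-treatment emergent, that is, "after the last assessment on Day 4 in Part1, and after Day 2 in Part 2".

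**Reporting (section 9.6.2.4).** "Only treatment emergent AEs will be presented in summary tables". These tables give the number and percentage of subjects and the number of events, overall and by system organ class, preferred term, causality and intensity. Pre-treatment and post-treatment AEs are only listed.

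**The concern.** The recording rule and the definition disagree about improvement. The definition asks for worsening before a pre-treatment AE counts. The recording rule asks only for a change, then issues a new record with a new onset. If that onset falls after the start of infusion, the new record looks like any other AE that began on treatment.

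Type, frequency and intensity of AEs is the first endpoint listed in section 2.2, and the Part 2 arms are small: the trial "will include 16 patients receiving FE 204205 and 4 patients receiving placebo". An event that got better after dosing would be shown as one that emerged on treatment. It would also need its own causality entry. Under section 9.6.2.4 a missing causality is treated as related, so an improvement could even appear as an adverse drug reaction.

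**Working it through.** The plan gives no figure on this point, so there is nothing to reproduce. The check is to apply the stated rules in order.

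**Step 1: which events can be split.** Onset must precede the first IMP administration, which is Day 1 in both parts. Section 8.2.2 grades intensity as mild, moderate or severe, and treats recovery as an outcome rather than a grade. A mild event therefore cannot improve without resolving, and resolution simply closes the single record. An improvement creates a second record only when a moderate or severe event drops at least one grade and continues.

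**Step 2: how the second record is classified.** Its onset is the time of change. The general limb has no intensity condition, and the trial-specific rule covers all AEs in the window. The worsening condition sits in a limb joined by *or*, so it adds cases and removes none.

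**Step 3: every combination of timing and direction.**

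| Time of intensity change | Direction | TEAE records as written | TEAE records if only worsening counts |
|---|---|---|---|
| Before first dose | Worse | 0 | 0 |
| Before first dose | Better | 0 | 0 |
| Start of infusion to last assessment on Day 4 (Part 1) or Day 2 (Part 2) | Worse | 1 | 1 |
| Same window | Better | **1** | **0** |
| After the window | Worse | 0 | 0 |
| After the window | Better | 0 | 0 |

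The two readings differ in one cell: improvement inside the window.

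**Step 4: where this could arise.** On Part 2 Day 1, the procedure described in section 6.1 (Visit 2) and applied through section 6.2 places sedation, jugular puncture, pulmonary artery and hepatic vein catheterisation and a contrast check before the first infusion. A moderate complaint from these steps that eases to mild by the Day 2 assessment fits the cell. In Part 1 the only source is an AE that starts between consent and the Day 1 infusion.

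**Step 5: size per subject.** The number of events always rises by 1. The number of subjects with any TEAE rises by 1 only if the subject has no other TEAE. In that case:

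- placebo, Part 2: 1/4 = 25 percentage points
- active, Part 2: 1/16 = 6.25 percentage points
- Part 1, all six patients: 1/6 = 16.7 percentage points

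**The case against.** The strongest reply is that section 8.1 already states the intended test for a pre-treatment AE, namely worsening, and that a general limb should not be read to defeat it. As evidence of intent, this stands. It does not settle the classification, because the recording rule turns the continuing event into a separate AE with its own onset, and nothing in the protocol links the pair or removes a second record of lower grade.

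Section 9 also leaves analysis detail to a separate SAP, whose text is not part of the document reviewed. A derivation rule there could correct the tables. Sites would still be told to create the records.

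Third, the AE analyses are descriptive, no decision rule rests on an AE rate, and all AEs are listed by subject, so a split pair would be visible. This stands and limits the consequence.

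A reader might also infer more than the documents support:

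- **That Part 1 Day 3 catheterisation adds cases.** Those patients were first dosed on Day 1, so a complaint before the Day 3 infusion is already treatment emergent and is never split.
- **That background symptoms of cirrhosis add many cases.** Section 8.1 records pre-existing conditions diagnosed at screening as medical history, and the split applies to AEs.
- **That recoveries become TEAEs.** Full recovery closes the record (Step 1).
- **That the first record's open outcome loses information.** The second record carries the final outcome.
- **That a share of Part 2 patients can be estimated.** A guess at how many have a complaint that eases would include those that resolve or ease within a grade, neither of which creates a second record.

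**Conclusion.** The point holds as a mismatch between the recording rule in section 8.2.2 and the definition in section 8.1. As written, a moderate or severe pre-treatment AE that drops a grade without resolving inside the window yields one TEAE record where the definition's own worsening test would yield none.

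The overall effect is probably small, because several conditions must coincide within a short window. The shifts in subject incidence (25 points on placebo, 6.25 on active) are per affected subject and assume no other TEAE in that subject. How often this would happen cannot be derived from the documents. The conclusion rests on the literal protocol text and on no corrective rule existing in the separate SAP. It is still worth correcting, because a stated rule misclassifies events for the first-listed endpoint and the remedy is simple.

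**What to change.** 1. In section 8.2.2 (Adverse Event), limit the two-record rule to pre-treatment AEs that worsen after the first IMP administration.
2. State there that a pre-treatment AE that improves stays as one pre-treatment record with its true outcome and outcome date.
3. In the TEAE derivation, state that a split record counts as treatment emergent only if its intensity exceeds the pre-dose intensity. Define pre-dose intensity as the grade at the start of the first infusion, so that an event which had already eased by then is judged against the right reference.

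The cost is a few words in section 8.2.2, one line in the eCRF completion guideline and one derivation rule. Events that worsen inside the window still count exactly as now, and improving events remain visible in the pre-treatment listing.

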### **Date and Time of Onset**

The date of onset is the date when the first sign(s) or symptom(s) were first noted. If the adverse event is an abnormal clinically significant laboratory test or outcome of an examination, the onset date is the date the sample was taken or the examination was performed.

### **Intensity**

The intensity of an adverse event must be classified using the following 3-point scale:

- Mild: Awareness of signs or symptoms, but no disruption of usual activity.
- Moderate: Event sufficient to affect usual activity (disturbing).
- Severe: Inability to work or perform usual activities (unacceptable).

### **Causal Relationship to IMP**

The possibility of whether the IMP caused the adverse event must be classified as one of the following:

#### Reasonable possibility:

There is evidence or argument to suggest a causal relationship between the IMP and the adverse event. The adverse event may occur as part of the pharmacological action of the IMP or may be unpredictable in its occurrence.

Examples:

- AEs that are uncommon but are known to be strongly associated with IMP exposure.
- AEs that are not commonly associated with IMP exposure, but the event occurs in association with other factors strongly suggesting causation, such as a strong temporal association or the event recurs on rechallenge.

### No reasonable possibility:

There is no reasonable evidence or argument to suggest a causal relationship between the IMP and the adverse event.

### Examples:

- known consequences of the underlying disease or condition under investigation.
- AEs common in the trial population, which are also anticipated to occur with some frequency during the course of the trial, regardless of IMP exposure.

### **Action Taken to IMP**

The action taken to the IMP in response to an AE must be classified as one of the following:

- No change (medication schedule maintained or no action taken)
- Withdrawn
- Interrupted
- Dose reduced
- Dose increased.

### **Other Action Taken**

AEs requiring therapy must be treated with recognised standards of medical care to protect the health and well-being of the subject. Appropriate resuscitation equipment and medicines must be available to ensure the best possible treatment of an emergency situation.

If medication is administered to treat the AE, this medication should be entered in the Concomitant Medication Log.

### **Date and Time of Outcome**

The date and time the subject recovered or died.

### **Outcome**

The outcome of an AE must be classified as one of the following:

- Recovered (fully recovered or the condition has returned to the level observed at initiation of trial treatment)
- Recovered with sequelae (resulted in persistent or significant disability/incapacity)
- Recovering (the event is improving)
- Not recovered
- Fatal.

### 8.3 Adverse Events of Special Interest

Taking into account the pharmacological profile of FE 204205, AEs related to exaggerated pharmacological effects, e.g. peripheral ischemia, increased blood pressure, and decreased cardiac output will be closely monitored.

### 8.4 Pregnancy and Pregnancy Outcome

If a pregnancy occurs, the subject will be withdrawn from the study and Global Pharmacovigilance at Ferring Pharmaceuticals informed, using an SAE Report Form. Note, that pregnancy itself is not an SAE. The mother and the foetus will be followed up at least until the birth of the infant and one month after the birth of the infant. In general, the follow-up will include the course, duration and the outcome of the pregnancy and the infant. If a pregnancy results in an abnormal outcome which the Investigator and/or Ferring consider to be related to the IMP, this outcome will be treated as an expedited report.

### 8.5 Serious Adverse Events

#### 8.5.1 Serious Adverse Event Definition

##### Serious Adverse Events during the Trial

An event is defined as a serious adverse event if it:	Guidance
results in death	Any event resulting in a fatal outcome must be fully documented and reported, including deaths occurring within four weeks after the treatment ends and irrespective of the causal relationship to the IMP. The death of a subject enrolled in a trial is per se not an event, but an outcome.
is life-threatening	The term life-threatening refers to an AE in which the subject was at immediate risk of death at the time of the event. It does not refer to an event, which may have caused death if it were more severe.
requires in-patient hospitalisation or prolongation of existing hospitalisation	The term hospitalisation means that the subject was admitted to hospital or that existing hospitalisation was extended as a result of an event. Hospitalisation describes a period of at least 24 hours. Over-night stay for observation, stay at emergency room or treatment on an out-patient basis do not constitute a hospitalisation. However, medical judgement must always be exercised and when in doubt the case should be considered serious (i.e. if case fulfils the criterion for a medically important event). Hospitalisations for administrative or social purposes do not constitute an SAE. Hospital admissions and/or surgical operations planned before trial inclusion are not considered adverse events, if the illness or disease existed before the subject was enrolled in the trial, provided that the condition did not deteriorate during the trial.
results in persistent or significant disability/incapacity	Disability/incapacity means a substantial disruption of a person's ability to conduct normal life functions. In doubt, the decision should be left to medical judgement by the Investigator.

An event is defined as a serious adverse event if it:	Guidance
is a congenital anomaly/birth defect	Congenital anomaly/birth defect observed in any offspring of the subject conceived during treatment with the IMP.
is an important medical event	Important medical events are events that may not be immediately life-threatening or result in death or hospitalisation but may jeopardise the subject or may require intervention to prevent one of the other outcomes listed in the definition above. Examples of important medical events include AEs that suggest a significant hazard, contraindication or precaution, occurrence of malignancy or development of drug dependency or drug abuse. Medical and scientific judgement should be exercised in deciding whether events qualify as medically important.  Important medical events include any suspected transmission of an infectious agent via a medicinal product. Any organism virus or infectious particle (e.g. prion protein transmitting Transmissible Spongiform Encephalopathy), pathogenic or non-pathogenic, is considered an infectious agent. A transmission of an infectious agent may be suspected from clinical symptoms or laboratory findings indicating an infection in a subject exposed to a medicinal product.

### **8.5.2 Collection, Recording and Reporting of Serious Adverse Events**

#### **SAE Reporting by the Investigator**

All SAEs must be reported **immediately** to Ferring Global Pharmacovigilance as soon as it becomes known to the Investigator and not later than within 24 hours of their knowledge of the occurrence of an SAE.

The Investigator is responsible for submitting the completed SAE Report Form with the fullest possible details **within 3 calendar days** of his/her knowledge of the SAE.

The SAE Report Form is included in the eCRF system, and must be completed and submitted according to the instructions provided on the form. In case the eCRF cannot be accessed and hence the SAE Report Form cannot be filled in within the eCRF system, a paper SAE Report Form should be used and sent to Ferring Global Pharmacovigilance using the contact details below.

Global Pharmacovigilance, Ferring Pharmaceuticals A/S  
E-mail: [[contact]](mailto:[contact])  
Fax: [REDACTED]

Completion of the Demographics, Adverse Event Log, Medical History Log and Concomitant Medication Log are mandatory for initial reports and for follow-up reports if any relevant changes have been made since the initial report. Data entries must have been made in the eCRF for Ferring Global Pharmacovigilance to access the information.

Additional information relevant to the SAE such as hospital records, results from investigations, e.g. laboratory parameters (that are not already uploaded in the eCRF), invasive procedures, scans and x-rays, and autopsy results can be faxed or scanned and e-mailed to Ferring Global Pharmacovigilance using the contact details in the section above. In any case this information must be supplied by the Investigator upon request from Ferring. On any copies provided, such details such as subject's name, address, and hospital ID number should be concealed and instead subject number should be provided.

The Investigator will supply Ferring and the IEC with any additional requested information such as results of post-mortem examinations and hospital records.

### **Expedited Reporting by Ferring**

Ferring will report all adverse events that are **serious, unexpected and with a reasonable possible causality to the IMP** as judged by either the Investigator or Ferring to the relevant parties within the stipulated timelines.

SAEs will be considered reportable regardless of whether or not the IMP was used in accordance with the provisions in the protocol, Investigator's Brochure and labelling.

#### Expedited Reporting

All AEs that are serious, unexpected and considered related to the IMP judged by either the Investigator or Ferring require expedited reporting. The expectedness is assessed by Ferring according to the Investigator's Brochure.

All available information relevant to the evaluation of the SAE will be reported. SAEs will be considered reportable regardless of whether or not the IMP was used in accordance with the provisions in the Protocol and/or the Investigator's Brochure. AEs that are serious but expected (related and/or unrelated to the IMP) are subject to expedited reporting in accordance with local requirements.

#### Timelines

Fatal or life-threatening serious, unexpected, related cases occurring in clinical investigations qualify for very rapid reporting. Regulatory agencies shall be notified (e.g., by telephone, facsimile transmission, or in writing) as soon as possible, but no later than 7 calendar days after first knowledge by the Sponsor that a case qualifies for expedited reporting, followed by a report that must be as complete as possible within 8 additional calendar days.

Serious cases that are unexpected and related and are not fatal or life-threatening, must be submitted as soon as possible but no later than 15 calendar days after first knowledge by the Sponsor that the case meets the minimum criteria for expedited reporting.

